## 7.5 Adjustments for Multiple Comparisons

No adjustments for multiple comparisons or multiple looks at data will be performed.

## 7.6 Demographic and Other Baseline Characteristics

Descriptive summary statistics will be used to summarize demographic and baseline characteristic variables for FAS. This will include mean, standard deviation, median, IQR, minimum, and maximum for continuous variables, and counts and percentages for categorical variables. These statistics will be presented by arm.

Demographic and baseline variables will be collected through: Demographic information, medical history, and baseline ECG and ECHO. Medication started prior to the date of randomization will also be summarized.

## 7.7 Treatment Characteristics

Concomitant medications will be summarized descriptively by arm using counts and percentages.

Medications will be reported by time of occurrence (prior to the study enrollment or initiated during the study execution).

Reason for system modifications will also be presented by listing.

## 7.8 Interim Analyses

No interim analyses are planned for this study.

## 7.9 Evaluation of Objectives

Endpoints defined in the section 4.2 will be used to evaluate objectives.

A device data quality analysis will be performed before the derivation of the analysis variables. Endpoints based on device data could be biased by the not compliance of the device data interrogation process compared to the clinical investigation plan.

### 7.9.1 Primary Endpoint

The time to persistent AF, defined as more than 7 consecutive days of AF, retrieved by using the device AT/AF diagnostics, or time to permanent AF. Time 0 for the time to event calculation is defined as the enrollment date or the first day in sinus rhythm after enrollment. Kaplan-Meier plots will be presented for the time to persistent AF together with table with survival probabilities and 95% confidence intervals estimated using complementary log-log method, for each randomization arm, if the number of followed-up patients and observed events will be adequate. Descriptive

statistics will be presented for time to persistent AF. No formal hypothesis testing nor Hazard Ratio (HR) calculation is planned in this analysis.

### 7.9.2 Secondary Endpoints

The time-to-event outcomes defined in section 4.1.2 will be summarized using Kaplan-Meier plots, tables with survival probabilities and 95% confidence intervals estimated using complementary log-log method, for each randomization group, if the number of followed-up patients and observed events will be adequate. Descriptive statistics will also be presented for the time-to-event outcomes. No formal hypothesis testing nor HR calculation is planned. Details about all time-to-event variables will be listed.

Counts and percentages will be used for categorical variables, for each randomization arm. Continuous variables will be summarized by descriptive statistics as described in the section 7.2.1.

Annual rates will be calculated for appropriate endpoints together with their 95% confidence interval (95%CI), for each randomization group, if the number of followed-up patients and observed events will be adequate.

Since the study was terminated early with small number of patients enrolled (less than 10% of expected sample size), the evaluation of persistent AF in patients with sick sinus syndrome compared to the one found in the Minerva trial, and the characterization the difference between the European and Indian populations, and the evaluation of the efficacy of atrial ATP therapies as a function of the device type (IPG, ICD, CRT-D, CRT-P), and population characteristics (baseline characteristics, implant indications) would not be robust: thus, the analyses will not be performed.

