Finally, a sub-analysis of the MINERVA trial, which analyses patients with paroxysmal or persistent AF, shows that ATP therapies are associated with a significantly reduction of AF early recurrence, compared with patients without ATP. [25] Furthermore, the percentage of early recurrence among ATP patients is significantly lower (20%) after episodes successfully terminated by ATP than episodes in which ATP therapies are not successful (39%) [25]. In addition, a more frequent reduction in left atrial diameter (LAD) has been noticed among ATP population. All these data suggest that ATP may reverse electrical and mechanical atrial remodeling, reducing the AF episodes recurrence.

Nowadays, small evidences on ATP programming optimization have been reported in literature.

The results from the PITAGORA trial showed that the ATP efficacy in interrupting atrial tachyarrhythmias is function of arrhythmia cycle length, type of ATP therapy delivered, and number of sequences delivered [26]. If considering the relationship between ATP therapy and arrhythmia cycle length, Ramp therapy showed a significant increase in ATP efficacy as per arrhythmias cycle length increase, while a flat relation for Burst+ therapy was found. In general, Ramp therapy was associated with a higher termination efficacy than Burst+ therapy in AT episodes with cycle length > 240 ms. Furthermore, a higher efficacy of Ramp therapy was evident within the first six sequences, whereas subsequent ATP attempts showed comparable performances for both therapies. So, additional evaluations are required to understand which ATP programming in terms of efficacy is the best in interrupting the arrhythmia and improving battery longevity.

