9.1.1. Baseline visit

Subjects may be enrolled into the study only after a minimum of 6 weeks from implant, or after leads stabilization (based on physician's discretion), to be sure about leads fixation.

During the baseline visit, the subject will be randomly assigned to one of the two study groups: intervention arm or control arm. If the atrial ATP therapies are already ON at the time of the randomization, the setting will be changed according to the assigned arm.

After enrolling the patient, the following data will be collected:

- **Demographics**, such as age and gender;
- **Medical History**, such as etiology, history of cardiovascular and arrhythmia events and surgical intervention as well as history of co-morbidities will be documented after enrolling a patient;
- Symptoms;
- **Device Data**, comprehensive of:
 - arrhythmic episodes stored in the device memory;
 - clinically significant changes in Cardiac Compass parameters (as per physician's opinion);
 - electrical parameters (leads impedance, sensing, threshold);
 - AT/AF therapies programming setting;

- ECG data: At the time of baseline (where available) from the patients' medical records (if done on the same day or ± 1 month from the date of the visit)
- **Echocardiographic (ECHO) data** obtained by performing an ECHO test (where available):
 - The test can be done on the same day of the baseline assessment, if recommended;
 - retrieving a previous ECHO exam not older than 1 month (± 2 weeks) from the baseline assessment;
 - scheduling an ECHO test in 1 month (± 2 weeks) from the baseline assessment;

- Medications.

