#### 4.2.2 Secondary Endpoints

1. To compare the two atrial ATP Programming arms in terms of clinical endpoints reported below:
  - all-cause death (at the end of 24 months), measured as time to event;
  - cardiovascular hospitalization (HF, AF or other), measured as time to first event and annual rate;
  - Annual rate for all-cause hospitalization;

- AT/AF burden metrics, measured in terms of time to first event (daily burden  $\geq 1$  day,  $\geq 2$  days,  $\geq 30$  days) or the ratio between time in AT/AF and the observation period;
  - number of successful and unsuccessful treated AT/AF episodes out of detected episodes;
  - number of delivered therapies per episode;
  - number of ATP sequences;
  - stroke, TIA or other thromboembolic events;
  - LA diameter (where available);
  - percentage of patients treated by anticoagulation therapy according management guideline;
  - electrical or pharmacological cardioversions, measured as time to first event and annual rate;
  - biventricular pacing percentage (in CRT-P /CRT-D patients).
2. Composite endpoint made of death, cardiovascular hospitalizations, stroke, TIA or other thromboembolic events;
  3. To evaluate the incidence of persistent AF in patients with sick sinus syndrome compared to the one found in the Minerva trial, and characterize the difference between the European and Indian populations;
  4. To evaluate the efficacy of atrial ATP therapies as a function of the device type (IPG, ICD, CRT-D, CRT-P), and population characteristics (baseline characteristics, implant indications).

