## 7.2 General Methodology

### 7.2.1 Statistical Methodology

All summary statistics will be presented by the actual randomization arm. FAS will be the main analysis set used for the analysis.

Descriptive statistics will be used to summarize patient demographics and baseline characteristics, medical history, procedure data, and other relevant study data. Mean and standard deviation, minimum, maximum, and median with the interquartile range (IQR) will be used for continuous

variables. Counts and percentages will be presented for categorical variables. Summary statistics will be reported with the same number of decimal places as original data collected.

Since the study was terminated early, also the primary and secondary endpoints will be analyzed with descriptive statistics without testing formal hypotheses.

For time-to-event analysis, if the number of observed events will be adequate, the Kaplan-Meier plots will be plotted by arm but only with a descriptive purpose. The survival probabilities at each follow-up visit will be calculated using Kaplan-Meier estimator together with 95% confidence intervals (using complementary log-log method) and will be presented in a table by arm for descriptive purpose.

Statistical analysis will be conducted in SAS version 9.4 or above (SAS Institute, Cary, NC).

Any deviations from the SAP will be described and justified in the Clinical Study Report

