### **7.2.2 Derived Variables**

Variables to evaluate the primary endpoint, as well as daily AF burden metrics, number of successful and unsuccessful treated AT/AF episodes out of detected episodes, number of delivered therapies per episode, and number of ATP sequences will be derived from the device datasets and will be described in detail in the SPR (ref).

The exposure time (months) for the time to first persistent AF will be computed from the date of randomization to the date of the last device save to disc for patients without persistent AF recurrence or to the date of first recurrence of persistent AF recurrence otherwise  $[(\text{data end} - \text{data in})/30.4]$ .

Variables to evaluate secondary endpoints as all-cause death, cardiovascular hospitalization (HF, AF or other), stroke, TIA or other thromboembolic events and annual rate for all-cause hospitalization will be derived from the adverse event dataset and will be described in detail in the SPR (ref).

The exposure time (months) for the secondary endpoints will be computed from the date of randomization to the date of the notice (follow-up visit or adverse event) for patients without events or to the date of the specific event otherwise  $[(\text{data end} - \text{data in})/30.4]$ .

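### The SAP specifies only level statistics for LA diameter and no within-patient change, although a baseline echo is collected where available and echo is optional at every visit

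*SAP*

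**What the plan says.** SAP 4.2.2 lists the endpoint as "LA diameter (where available"), with no time point and no statement of whether the level or the change is meant. SAP 7.9.2 then gives one rule for all such endpoints: "Continuous variables will be summarized by descriptive statistics as described in the section 7.2.1". Section 7.2.1 supplies the content: "Mean and standard deviation, minimum, maximum, and median with the interquartile range (IQR) will be used for continuous" variables, presented by randomised arm. The same section explains the restraint: "Since the study was terminated early, also the primary and secondary endpoints will be analyzed with descriptive statistics without testing formal hypotheses".

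On data collection, Protocol 9.1.1 and 9.1.2 and Table 1 schedule echo at baseline and at 6, 12, 18 and 24 months, each time only where available. SAP 7.6 names the baseline echo as a source for the baseline summaries, which are given by arm. Protocol 9.1.1 allows three sources for the baseline echo: one done on the day, an earlier one up to about a month old, or one scheduled about a month (give or take two weeks) after the visit.

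In the background, Protocol 4.1.5 reports from a MINERVA sub-analysis that "a more frequent reduction in left atrial diameter (LAD) has been noticed among ATP population".

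**The concern.** With a baseline table by arm and follow-up summaries by arm, a reader will compare the two and read the difference as change. That is safe only if the same patients contribute to both. Because echo is optional, they need not, and no echo count or paired count is promised. In arms of 37 and 38, selective return for echo could create or hide a trend over time. If the selection differs between arms, it could create or hide an apparent difference in trend between them.

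The result the protocol cites about LA diameter concerns reduction, which is a within-patient quantity. Level summaries cannot show it. The baseline value that would show it is already being collected where available.

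The baseline echo also has a dating problem. Randomisation and reprogramming take place at the baseline visit, so an echo scheduled a month later is measured under the assigned programming. The SAP has a pre-randomisation rule for baseline medications (7.6) but none for echo.

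**Working it through.** The plan states no figure for LA diameter, so there is none to reproduce. The check has three parts.

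**1. Is change or pairing specified anywhere?**
- SAP 7.9.2 points to 7.2.1, and 7.2.1 lists level statistics. Neither mentions change, paired values or the endpoint's own baseline.
- SAP 7.2.2 defers AF burden, treated-episode counts, therapy and sequence counts, and several adverse-event outcomes to the separate programming document (SPR). LA diameter is not among the deferred variables.
- SAP 7.6 uses the baseline echo, but only as a baseline summary.

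**2. How far can means move with no true change?** Let *f* be the share of patients with a baseline echo who also have the follow-up echo. Let *d* be the baseline difference between those who return and those who do not. If nobody changes:

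- baseline mean = f·m₁ + (1 − f)·m₀
- follow-up mean = m₁
- apparent change = (1 − f)(m₁ − m₀) = (1 − f)·d

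Assuming d = 3 mm:

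| f | Apparent change | Paired change |
|---|---|---|
| 0.8 | 0.6 mm | 0 |
| 0.5 | 1.5 mm | 0 |
| 0.3 | 2.1 mm | 0 |

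The limit as f approaches 0 is 3 mm. Results scale with d, which the documents do not give.

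**3. What precision would the paired summary have?** Assumptions: SD 6 mm at both times, 15 pairs per arm, baseline-to-follow-up correlation r.

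- Within-arm mean change: SE = 6·√(2(1 − r)/15); 95% half-width = 2.145 × SE (t, 14 df).
- Arm contrast on follow-up levels: SE = 6·√(2/15) = 2.19 mm.
- Arm contrast on change: 2.19·√(2(1 − r)).
- Arm contrast adjusted for baseline (ANCOVA, large-sample): 2.19·√(1 − r²).

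| r | Within-arm SE (half-width), mm | Contrast SE, levels | Contrast SE, change | Contrast SE, ANCOVA |
|---|---|---|---|---|
| 0.3 | 1.83 (3.9) | 2.19 | 2.59 | 2.09 |
| 0.5 | 1.55 (3.3) | 2.19 | 2.19 | 1.90 |
| 0.7 | 1.20 (2.6) | 2.19 | 1.70 | 1.56 |
| 0.8 | 0.98 (2.1) | 2.19 | 1.39 | 1.31 |

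Free of the SD and pair-count assumptions: with all 38 and 37 patients, the 95% half-width for a contrast of levels is 1.96·√(1/38 + 1/37) = 0.453 SD. For change it is 0.536 SD at r = 0.3 and 0.351 SD at r = 0.7. Change scores therefore lose precision for an arm contrast when r is below 0.5 and gain when it is above.

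**The case against.** The strongest reply is that the SAP is openly descriptive. The trial stopped at 75 of 758 patients, and no test, interval or between-arm estimate is planned for any continuous variable. A reader might infer that the plan wastes precision, but no contrast is planned whose precision could be wasted. That part of the reply stands. Column 2 of the second table is the relevant one; the contrast columns only illustrate an optional supplement.

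Next, the SAP never says that follow-up levels alone will be shown. That is an inference from silence, and SAP 9.1 places the table shells in the SPR, which is not available here. This stands as a limit on what can be claimed. It is not a full answer, because the choice between level and change defines the summary and belongs in the SAP.

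A reader might also extend the point to AT/AF burden and biventricular pacing percentage. The documents do not support that:
- Burden is defined as a time to first event "or the ratio between time in AT/AF and the observation period", and no baseline window is given. The baseline visit does collect "arrhythmic episodes stored in the device memory", but no baseline burden variable is derived from it.
- Biventricular pacing percentage is not listed among the baseline device data in Protocol 9.1.1.
- Eighteen months is the limit on implant age at enrolment. It is not a stated length of device record.

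The MINERVA sentence is background and is not given as the rationale for this endpoint. Finally, pairing does not remove selection: patients with two echoes may be unusual. It only prevents a change in who is measured from appearing as change.

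Against all this, SAP 7.9.2 already plans 95% intervals for survival probabilities and annual rates. An interval on a mean change is therefore within the spirit of the report.

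**Conclusion.** The point holds for LA diameter. The SAP specifies only level statistics, does not pair them with the baseline echo it already tabulates, and sets no date rule for that echo. Differences between visit means can therefore reflect who was measured. In the illustration the artefact is 0.6 to 2.1 mm. That range rests on an assumed 3 mm starting difference and return rates of 0.8 to 0.3, and the true size cannot be judged from the documents.

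This is a cheap improvement to one optional secondary endpoint and has no bearing on the primary endpoint. A reader might infer a broader fault covering three endpoints with a quantified loss of precision. The documents do not support that, because a baseline value is clearly collected only for LA diameter (where available) and no arm contrast of continuous variables is planned.

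**What to change.** In SAP 7.9.2, for LA diameter, alongside the planned level summaries:

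- Report within-patient change from baseline by arm and visit, in patients with both values, with the paired n and a 95% CI.
- Take baseline from echoes dated on or before randomisation. Show patients whose baseline echo was done afterwards, as Protocol 9.1.1 permits, separately or as a sensitivity summary.
- Optionally, if the paired n allows, add baseline-adjusted arm means, labelled as descriptive.
- Extend the same treatment to the AT/AF burden ratio and biventricular pacing percentage only if a pre-randomisation value exists in the device data.

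The cost is a few lines of SAP text and one table, with no new data. If the SAP is not reissued, 7.2.1 already allows a deviation to be described and justified in the study report. The drawbacks are that paired summaries use fewer patients, selection into having an echo remains, and change is less precise than level for an arm contrast if the correlation is below 0.5. Keeping the level summaries alongside lets the reader see all measured patients.

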### 7.10 Safety Evaluation

Adverse events (AEs), adverse device effects (ADEs) and device deficiencies (DDs) will be presented using the MedDRA coding and presented by tables and listings. The Adverse events will be presented using system organ class and/or preferred term. Counts and percentages will be used to summarize adverse events and device deficiencies. Tables will be repeated for serious adverse events (SAEs), serious adverse device effects (SADEs), unanticipated serious adverse device effects (USADEs) if applicable. Cardiovascular related AEs will be presented in a separate table.

Apart from that, time, severity, relation to procedure, action taken, and outcome will be presented descriptively in a separate table.

Deaths and reasons for death will be summarized descriptively using counts and percentages.

Detailed listings will be prepared for adverse events, deaths, and device deficiencies, if needed.

### 7.11 Health Outcomes Analyses

No specific health outcomes analyses are planned for this study.

## 7.12 Changes to Planned Analysis

The original analysis described in CIP assumed that the study would recruit 758 patients and formal hypotheses would be tested. Due to early termination of the study, the formal hypothesis testing will not be conducted in the analysis and only descriptive statistics and figures will be presented. A final decision on the study endpoints evaluation will be taken only when the complete set of clinical and device data will be collected and evaluate in terms of quality and reliability.

## 8. Validation Requirements

---

All collected data will be reviewed for completeness, correctness, and consistency. In case of issues, queries will be sent to the investigator to complete, correct or comment on the data. To ensure the quality of the results provided for the study in the form of tables, listings and figures, and the derived datasets the following processes are used:

- Statistical programming and analysis will be done by qualified programmer(s) and statistician(s) following applicable procedures and best practices;
- The derived datasets will be validated by a second programmer or statistician;
- The tables will be validated by a second programmer or statistician;
- Statistical results will be reviewed and confirmed by a second statistician.

The entire set of tables, listings, and figures (TLF) will be 100% checked for accuracy, completeness, and consistency prior to inclusion in the final clinical study report.

According to Medtronic SOPs the level II validation (the peer reviewer reviews the code; where appropriate, performs manual calculations or simple programming checks to verify the output) will be implemented for both Datasets and TLFs.

## 9. Statistical Appendices

---

### 9.1 Tables, Listings and Figures

Detailed list and mock TLF shells used for this study can be found in SPR Mandate AF document v 1.0 27-AUG-2021 or later version.

## Summary of Changes

Version	Effective Date	Summary of Changes	Change Author
1.0	27-AUG-2021	Initial Release	[name], [name]
